1.2.3 Clinical Experience

Study APX005M-001 is a first in human phase 1 dose escalation study of APX005M with 8 pre-planned dose levels. APX005M was administered to study subjects at doses up to 1 mg/kg. At the 1 mg/kg dose level, 1 out of 6 dose limiting toxicity (DLT)-evaluable subjects experienced a DLT (grade 4 cytokine release syndrome). Two additional subjects at the 1mg/kg dose level experienced serious adverse events (SAE) in later cycles (Grade 3 cytokine release syndrome and Grade 4 thrombocytopenia). On May 2, 2016 Apexigen decided to discontinue dose escalation and enroll up to 6 subjects in dose level 0.6 mg/kg (originally designed as an intermediate de-escalation dose level) and an additional 3 subjects at the previously completed dose level 0.3 mg/kg to better characterize the safety and pharmacodynamics (PDn) of APX005M and to help establish the single agent recommended phase 2 dose (RP2D). The RP2D for APX005M as a single agent every 21 days is 0.3 mg/kg body weight.

APX005M demonstrated a dose-dependent activation of APCs (as demonstrated by increases in expression of activation markers such as CD54, CD70, CD80, CD86, HLA-DR), T cell activation and increases in circulating levels of IL12, INF- γ , TNF- α and IL6.

For further details on the APX005M-001 study and the overall safety of APX005M please refer to latest version of the APX005M Investigator's Brochure [16].

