1.2.4 Summary of the Known and Potential Risks and Benefits

Symptoms associated with cytokine release syndrome (including but not limited to flushing, itchiness, chills, fever, rash, tachycardia, hypotension, hypertension, rigor, and myalgia) after administration of APX005M are possible and have been observed in some of the subjects receiving APX005M. Guidance for monitoring and management of cytokine release syndrome are included in this protocol and in the APX005M Investigator's Brochure.

Transient transaminase elevations (\leq Grade 2) have been observed in several subjects with liver metastases, which were not associated with a particular dose of APX005M. Six subjects with liver metastases enrolled in the study experienced a transient increase in total bilirubin. Liver function test abnormalities tend to resolve to baseline within 7 days from APX005M administration.

Transient decreases in peripheral blood lymphocyte count in general and B-cell count in particular have been observed for APX005M as well as for other CD40-agonistic mAbs, and are believed to be a PDn effect. Transient decreases in platelet counts were observed for some of the subjects receiving higher doses of APX005M but were not associated with bleeding or other clinical manifestations.

Other symptoms might also occur, including allergic reactions, which could be severe, pulmonary edema, and rarely, thromboembolic events, myocardial infarction and/or death.

In the recently completed Phase 1 study APX005M-001, APX005M demonstrated a dose-dependent activation of APCs, T cell activation and increases in circulating levels of cytokines.

The biological effects and the overall tolerability of APX005M up to 1mg/kg body weight suggest a best in class profile for APX005M and the possibility of a safe and tolerable combination with other immunomodulatory antibodies such as nivolumab.

Please refer to the most recent version of the APX005M Investigator Brochure for the most current summary of APX005M to date.

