Escalation Dose Level	DL1	DL2		DL3
De-escalation Dose Level			DL2a	
APX005M mg/kg body weight	0.03	0.1	0.2	0.3
Minimum number of DLT evaluable subjects	3	3	3	3

Abbreviations: DL = dose level; DLT = dose-limiting toxicity.

The DLT observation period for dose escalation is the 21 days following the first administration of APX005M and nivolumab (first 3-week cycle). Safety and tolerability of the APX005M and nivolumab combination will be monitored by representatives from Apexigen and the Investigators on a regular basis and prior to each dose escalation.

Dose escalation will continue if 0 out of 3 evaluable subjects experience a DLT during the DLT observation period (i.e., <33% DLT-evaluable subjects in that cohort have a DLT). If 1 DLT-evaluable subject in any DL cohort experiences a DLT, that cohort will be expanded to include additional 3 DLT-evaluable subjects (i.e. a total of 6 evaluable subjects). Dose escalation will continue if 1 out of 6 evaluable subjects experience a DLT during the DLT observation period (i.e., <33% DLT-evaluable subjects in that cohort have a DLT). Decision to open a new DL cohort will be based on the totality of the data available at that time.

The MTD is the maximum dose of APX005M combined with 360 mg of nivolumab for which <33% of DLT-evaluable subjects experience a DLT.

If the DLT rate in DL 3 exceeds 33%, or 2 or more subjects in DL 2 experience a Grade 2 infusion reaction/cytokine release syndrome, or at the discretion of the sponsor, the intermediate lower DL 2a will be evaluated (de-escalation). Up to 6 subjects can be enrolled in any of dose levels below the MTD or highest DL tested, should sponsor decide to discontinue dose escalation prior to reaching the MTD.

The RP2D will be based on the overall safety and tolerability of the combination of APX005M and nivolumab.

Phase 2 dose-expansion:

After identification of the RP2D of APX005M in combination with nivolumab 360 mg IV every 21 days, study will continue with 3 cohorts.

- Cohort 1: inNSCLC
- Cohort 2: PD1-MM
- Cohort 3: PD1-NSCLC
 - Group A
 - Group B

[figure not shown]
Each cohort and group of the Phase 2 dose-expansion portion of the study will follow a Simon optimal 2-stage design. Subjects treated at the RP2D in the dose-escalation portion will be included in Stage 1 of the relevant cohort. Additional subjects will be enrolled for a total of 24

subjects in Cohort 1 and 12 subjects in each of Cohort 2, Cohort 3 Group A and Cohort 3 Group B.

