Subjects will be evaluated for tumor response approximately every 8 weeks following the first dose of investigational product. Subjects that are non-evaluable for tumor response (see definition in [Section 7.2](#)) will be replaced. An ORR [complete response (CR) + partial response (PR)] of at least 22% (6 confirmed out of 24 response evaluable subjects) in the inNSCLC cohort and 5% (1 confirmed out of 12 response evaluable subjects) in the PD1-MM cohort or PD1-NSCLC (Group A or B) is required in Stage 1 for that cohort to proceed to Stage 2. Enrollment may continue into Stage 2 while the planned number of subjects for Stage 1 are followed for efficacy.

In Stage 2, an additional 21 subjects will be enrolled in Cohort 1 (inNSCLC) and an additional 25 subjects will be enrolled in each of Cohort 2 (PD1-MM) and Cohort 3 (PD1-NSCLC) Group A and B. The study schema is presented in [Figure 1](#).

Figure 1: APX005M-002 Study Design

A minimum of 6 subjects per cohort/group who have a primary or metastatic lesion that can be biopsied without interfering with subsequent tumor assessments and who consent to collection of paired tumor biopsies for tumor biomarkers should be enrolled during Phase 1b and Phase 2.

At any time during the study, enrollment will be suspended pending safety review if any of the following events occur since last safety review:

- ≥1 Grade 5 suspected adverse reaction (SAR) (for definition see [Section 6.1.2](#))
- ≥2 Grade 4 infusion reaction/ cytokine release syndrome

- ≥ 2 Grade ≥ 3 immune related AEs in more than 1 subject

Enrollment will resume following assessment by the Apexigen Medical Monitor, contract research organization Medical Monitor and lead Investigator.

For subjects that require confirmation of PD while on treatment with anti-PD-1/PD-L1 therapy, any of the following criteria must be met:

- ≥ 5 mm further increase in sum of measures of target lesion
- ≥ 5 mm further increase in sum of measures of new lesion
- further increase in the size of non-target lesion(s)
- new non-target lesions
- appearance of new lesion(s) when none have previously been recorded
- increase in the number of new lesions
- all of the following
 - maintain $> 20\%$ increase in target lesion burden at confirmed PD scan relative to nadir (as per RECIST1.1)
 - target lesion burden at confirmatory PD scan greater than 90% of target lesion burden at unconfirmed PD (initial PD) scan (to account for intra-subject reader variability)

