3.7 Dose Modifications

Suspected adverse reactions (SAR) (for definition see [Section 6.1.2](#)) associated with APX005M and nivolumab exposure may represent an immunologic etiology. These AEs may occur shortly after the administration of investigational products or several months after the last dose of investigational product. Management of suspected adverse drug reactions may require treatment hold, dose reduction of APX005M, or discontinuation of one of both investigational products as per [Table 4](#). If a subject experiences several toxicities, the recommended dose modification should be based on the highest grade toxicity.

See [Section 3.4.1.2](#) for supportive care guidelines, including use of corticosteroids.

Table 4: Dose Modification Guidelines for Suspected Adverse Reactions

Toxicity	Grade	APX005M	Nivolumab
Neutropenia (± febrile)	3-4	Hold	Hold
Thrombocytopenia	3	Hold. Dose reduction if > 7 days	Hold
	4	Hold. Dose reduction	Hold. Discontinue if > 7 days
	3-4 with bleeding	Discontinue	Discontinue
Diarrhea/colitis	2	1 st occurrence: hold 2 nd occurrence: dose reduction	Hold
	3	1 st occurrence: dose reduction 2 nd occurrence: discontinue	Discontinue
	4	Discontinue	Discontinue
Uveitis, eye pain or blurred vision that does not improve to Grade 1 before next cycle	2-4	Hold	Discontinue
Increased bilirubin	2	Hold	Hold
	3-4	Discontinue	Discontinue
Increased AST, ALT	2	Hold	Hold
	3	Hold. Dose reduction For subjects with liver metastasis reduce dose only if Grade 3 > 72 hours	Discontinue
	4	Discontinue	Discontinue
Endocrinopathies	2	Hold	Hold
	3-4	1 st occurrence: Hold. Institute endocrine replacement therapy 2 nd occurrence: discontinue after consultation with Medical Monitor	1 st occurrence: Hold. Institute endocrine replacement therapy* 2 nd occurrence: discontinue after consultation with Medical Monitor
Nivolumab infusion reaction	2	Administer additional premedication. Increase infusion time to 90 min	1 st occurrence: continue 2 nd occurrence: discontinue
	3	Hold for 1 cycle. Continue single agent at following cycle	Discontinue
	4	Discontinue	Discontinue

Toxicity	Grade	APX005M	Nivolumab
APX005M infusion reaction/cytokine release syndrome	3	Hold. Dose reduction	Hold
	4	Discontinue	Discontinue
Pneumonitis	2	1st occurrence: hold 2nd occurrence: discontinue	1st occurrence: hold 2nd occurrence or if > 14 days: discontinue
	3-4	Discontinue	Discontinue
Creatinine elevation	2	Hold	Hold. Discontinue if > 7 days
	3	Hold	Hold. Discontinue if > 7 days

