6.3 Collection and Reporting

6.3.1 General AE Reporting

All AEs will be collected from the time the subject receives any investigational product through 30 days after receiving the last dose of investigational product, death, or initiation of new anticancer therapy, whichever occurs first. SAEs and AEs with potential immunologic etiology will be recorded up to 100 days and pregnancies up to 120 days after the last dose of investigational product, death, or initiation of new anticancer therapy, whichever occurs first.

Events that occur after the subject signs the informed consent but prior to the first dose of investigational product will be recorded as past medical history; events that start after the first dose of investigational product will be recorded as AEs. In addition, the Investigator should report any AEs that may occur after this time period which are assessed to have a reasonable possibility of being associated with investigational products.

All AEs must be promptly documented on the AE eCRF. The minimum information required for each AE includes event, duration (start and end dates), start time (for events occurring within 48 hours after the start of APX005M infusion) severity, seriousness, causality to investigational product, action taken, and outcome. Whenever possible, reporting specific diagnosis is preferred when reporting AEs in the AE eCRF rather than reporting individual signs and symptoms except for infusion related reactions and cytokine release syndrome.

All AEs that are considered related to investigational products must be followed to resolution, stabilization, until improvement is not expected, 30 days after receiving the last dose of investigational product, death, or initiation of new anticancer therapy, whichever occurs first. SSAR will be followed until resolution, stabilization, or until resolution is not anticipated.

If an office visit is not possible, a follow-up of ongoing AEs should be attempted by telephone and documented in the subject's source file. AEs continuing at 30 days after the last dose of investigational product should have a comment in the source file by the Investigator that the event has stabilized or is not expected to improve.

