5.4.3.3 Adverse Events

All AEs will be collected in the eCRF from the time the participant signs informed consent through 30 days after the last dose of investigational product, death, or initiation of new anticancer therapy, whichever occurs first. AEs will be coded to system organ (SOC) and preferred term (PT) using the MedDRA dictionary v18.0.

The NCI-CTCAE will be used to assess the severity of AEs.

The relationship of each AE to the investigational product will be classified as related or unrelated. If relationship is missing, the event will be listed as missing relationship but summarized as related.

Summaries will focus on the TEAEs. They will be summarized by dose level and overall for Phase 1b and by cohort and overall for Phase 2 (including participants treated at RP2D in Phase 1b). The following summary tables will be provided:

- An overall summary of the frequency of participants reporting all TEAEs, serious TEAEs, TEAEs with CTCAE grade 3 or higher, treatment-related TEAEs (separately for APX005M and nivolumab), and TEAEs leading to treatment discontinuation (separately for APX005M and nivolumab), TEAEs with fatal outcome.
- TEAEs by SOC and PT
- Serious TEAEs by SOC and PT
- TEAEs with CTCAE grade 3 or higher by SOC and PT
- Treatment-related TEAEs by SOC and PT (separately for APX005M and nivolumab)
- TEAEs leading to treatment discontinuation by SOC and PT (separately for APX005M and nivolumab)
- TEAEs with fatal outcome by SOC and PT
- TEAEs by SOC and PT, and by maximum CTCAE grade

All AEs will be listed by dose level (Phase 1b)/cohort (Phase 2, including participants treated at RP2D in Phase 1b), and then study site, participant number, and cycle day. Separate listings will be produced for TEAEs, serious TEAEs, TEAEs leading to APX005M discontinuation, delay, and interruption, and TEAEs with fatal outcome. Separate listings will be generated for immune-mediated events.

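### Infusion reactions and CRS are exempt from diagnosis-based AE reporting and the SAP has no step to rebuild episodes, so the tables it describes cannot give their incidence or maximum grade

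*Protocol*

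**What the plan says.** **Recording.** Protocol 6.3.1 asks sites to report a diagnosis where possible, "rather than reporting individual signs and symptoms except for infusion related reactions and cytokine release syndrome". The minimum data that it lists for each AE include severity, causality and dates, plus a start time if onset is within 48 hours of the start of the APX005M infusion. They do not include an overall grade for a reaction episode or a field that ties its symptoms together.

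**Rules that use a graded syndrome.** Protocol 2.2 suspends enrolment, pending review, on "≥2 Grade 4 infusion reaction/ cytokine release syndrome" since the last safety review. It opens dose level 2a if "2 or more subjects in DL 2 experience a Grade 2 infusion reaction/cytokine release syndrome", among other triggers. Table 4 in Protocol 3.7 has rows by grade for "APX005M infusion reaction/cytokine release syndrome" and, separately, for nivolumab infusion reaction.

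**Analysis.** SAP 5.4.3.3 lists its summaries by system organ class and preferred term, ending with "TEAEs by SOC and PT, and by maximum CTCAE grade". It adds separate listings for immune-mediated events. It names no grouped term, search or table for infusion reaction or CRS. The table shells are in an external file (SAP section 7).

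**The concern.** CRS is the first risk described in Protocol 1.2.4, and Protocol 1.2.3 reports it as the dose-limiting event at 1 mg/kg in the first-in-human study ("subjects experienced a DLT (grade 4 cytokine release syndrome"). A reader of the safety results will want to know how many subjects had a reaction and how severe the worst one was. If a subject has fever, rigor, tachycardia and hypotension after one infusion and the site enters what 6.3.1 suggests, the tables show four preferred terms, each with its own grade. Nothing in them says that these were one episode, or what grade it had as a whole.

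At stake is a secondary safety output, the incidence and severity of AEs, for the risk that the protocol itself manages most closely. A second matter is whether the suspension rule is counted the same way each time it is checked.

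**Working it through.** The documents give no incidence or error rate for infusion reaction or CRS, so there is no stated figure to reproduce. The check sets the texts side by side and then sizes the ambiguity under labelled assumptions.

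**Step 1: is an episode grade recorded?** Table 4 and Protocol 3.4.1.2 make the investigator grade the reaction in order to manage it. Protocol 6.3.1 does not require that grade in the AE record, and Protocol 6.2.2 grades each reported AE separately. The grade exists at the bedside but has no required place in the data.

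**Step 2: can the tables recover incidence?** Protocol 1.2.4 gives an open list of components: "Symptoms associated with cytokine release syndrome (including but not limited to flushing, itchiness, chills, fever, rash, tachycardia, hypotension, hypertension, rigor, and myalgia". Suppose that every row entry belongs to an episode and that every episode produces at least one row. Then

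largest row ≤ syndrome incidence ≤ min(1, sum of rows).

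With assumed rows of 30%, 30%, 10% and 10%, the lower bound is 30% and the upper bound is 0.30 + 0.30 + 0.10 + 0.10 = 80%. In practice fever or rash can have other causes, so even these bounds are optimistic. The rows carry no episode grade, so the maximum grade is not recoverable either.

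**Step 3: mixed practice.** If a share *s* of affected subjects is entered under the syndrome term and the rest by symptoms, the syndrome row shows *s* × true incidence. For an assumed true incidence of 30%, *s* = 0.75, 0.50 and 0.25 give 22.5%, 15% and 7.5%.

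**Step 4: what does the suspension rule count?** The rule says two or more Grade 4 events. The neighbouring rule on immune-related AEs requires more than one affected subject; this one does not. For illustration, let *p* be the assumed true Grade 4 rate per subject, *c* the assumed share recognised as a Grade 4 syndrome, and *n* the subjects in a review window. The review interval is not given, so *n* is set to planned stage and cohort sizes. The chance that the rule fires is P(X ≥ 2) with X ~ Binomial(*n*, *pc*). If symptom rows are counted and every affected subject has at least two Grade 4 rows, it is P(X ≥ 1) with X ~ Binomial(*n*, *p*).

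At *p* = 5%:

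| n | c = 1 | c = 0.75 | c = 0.50 | c = 0.25 | rows counted (upper limit) |
|---|---|---|---|---|---|
| 12 | 0.118 | 0.072 | 0.035 | 0.009 | 0.460 |
| 37 | 0.558 | 0.406 | 0.236 | 0.078 | 0.850 |
| 45 | 0.665 | 0.507 | 0.311 | 0.109 | 0.901 |

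For *n* = 37, *c* = 1 and *c* = 0.50 give 0.169 and 0.053 at *p* = 2%, and 0.896 and 0.558 at *p* = 10%. The counting convention can therefore move the rule in either direction.

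**The case against.** The other side has several good points.

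- **The sentence lifts a preference; it is not a ban.** A reader might infer that sites must not enter a syndrome term and that the CRS row will be zero. The text does not say so. This stands, but it leads to mixed practice, which Step 3 shows is also uninterpretable.
- **Serious events have their own route.** A life-threatening AE is serious (Protocol 6.1.4) and must be notified within 24 hours (6.3.3), and the Medical Monitor reviews safety information promptly (section 6). A reader might infer that the suspension count cannot be made. The documents do not support that: the rule is not tied to the SAP tables, and SAP 5.4.5 does not link its monthly outputs to it. What remains is that neither the record nor the unit of count is named.
- **Some separate output may exist.** Protocol 3.4.1.2 places infusion reaction/CRS among AEs of potential immunologic cause, so the immune-mediated listing may include it. Serious-event and DLT outputs capture qualifying cases. The external table shells were not available and might hold more. So it cannot be said that there is no separate output at all. But a listing is not an incidence, and the SAP text gives no derivation for one.
- **The dose level 2a trigger is historical.** SAP section 7 records that the Phase 1b report was completed under an earlier SAP version, and that trigger applied to a small, closely reviewed group.
- **Symptom capture looks deliberate.** The 48-hour start times match the symptom window in Protocol 3.4.1.2 and make episodes partly recoverable. This is true, and the fix uses it, but neither document plans that step.

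**Conclusion.** The point holds for the tables. As described in SAP 5.4.3.3, they cannot give the incidence or maximum grade of infusion reaction/CRS, and mixed site practice would understate the syndrome row. For the suspension rule the point is narrower: Grade 4 episodes should reach the sponsor, but the source record and counting unit are undefined.

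The size cannot be taken from the documents. The 30% to 80% range and the firing probabilities rest on assumed symptom rates, *p*, *c* and *n*, and show only how wide the ambiguity can be. The conclusion also assumes the natural reading of 6.3.1, and that neither the external shells nor the eCRF instructions already supply an episode grade or grouping.

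Three further inferences should not be drawn:

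- The four-week recovery rule in Protocol 4.1 names no grade and works with symptom-level entries.
- A lost comparison with APX005M-001 is not shown. The protocol reports CRS there as a DLT and a serious event, routes that also exist here, and does not say how non-serious reactions were recorded.
- Neither the length of the symptom list, which is open-ended, nor total planned enrolment measures the effect.

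**What to change.** 1. **Protocol 6.3.1 or the eCRF completion guideline.** Replace the exception with: record each infusion reaction or CRS episode as one AE under the diagnosis, with its overall CTCAE v4.03 grade, suspected product and start time; record component signs and symptoms as linked detail, not counted separately.
2. **SAP 5.4.3.3.** Add one table of infusion reaction/CRS episodes by maximum grade, cohort, cycle and suspected product.
3. **Suspension rule.** State that the existing rule is counted from the episode record, and state its counting unit. The threshold itself is not changed.
4. **Phase 2 data already entered.** Have the Medical Monitor flag episodes, using the start times held for events within 48 hours of the APX005M infusion. Nivolumab is given first, so a reaction before APX005M starts may have a date but no time; such cases need source review.

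The cost is one sentence, a linking field, one table, slightly more data entry per episode and one review pass. Symptom detail is kept.
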